9. EFFICACY

Analysis Set: Full Analysis Set (FAS)

9.1 Endpoints

9.1.1 *Primary Efficacy Endpoint:*

- Sputum culture conversion defined as at least three consecutive negative sputum samples during the treatment period.

9.1.2 *Secondary Efficacy Endpoints:*

- Sputum smear conversion defined as at least three consecutive negative AFB stained sputum smears on microscopy during the treatment period in subjects who were smear positive at Baseline.
- Durability of sputum culture conversion (defined as conversion at or before Week 48 and culture still negative at 12-weeks follow-up).
- Durability of sputum smear conversion (defined as conversion at or before Week 48 and smear still negative at 12-weeks follow-up).
- Change in semi-quantitative grade of number of NTM on microscopy of AFB stained sputum smears from Baseline to Weeks 4, 8, 12, 16, 20, 24, 28, 32, 36, 40, 44, 48 and 12-week follow-up.
- Change in semi-quantitative grade of sputum cultures from Baseline to Weeks 4, 8, 12, 16, 20, 24, 28, 32, 36, 40, 44, 48 and 12-week follow-up.
- Change in symptom scores (assessed using Lower Respiratory Tract Infections – Visual Analogue Scale (LRTI-VAS) and Quality of Life Questionnaire– Bronchiectasis (QOLB) from Baseline to Weeks 4, 8, 12, 16, 20, 24, 32, 40, 48 and 12-week follow-up.
- Change in Global Rating of Health (GRH) from Baseline to Weeks 4, 8, 12, 16, 20, 24, 32, 40, 48 and 12-week follow-up.
- Change in body weight from Baseline to Weeks 4, 8, 12, 16, 20, 24, 32, 40, 48 and 12-week follow-up.
- Change in 6MWD, oxygen desaturation and Borg CR10 scores during a 6MWT from Baseline to Week 12, 24, 48 and 12-week follow-up.

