| Dispense trial drug       |           | X                 | X                | X                | X                | X                 | X                 | X                 | (X)               | X                 | (X)               | X                 |                   |                   |                   | (X)                            |
| Return of used trial drug |           |                   | X                | X                | X                | X                 | X                 | X                 |                   | X                 |                   | X                 |                   | X                 |                   | (X)                            |
| Compliance                |           |                   | X                | X                | X                | X                 | X                 | X                 |                   | X                 |                   | X                 |                   | X                 |                   | (X)                            |
| AEs                       |           | X                 | X                | X                | X                | X                 | X                 | X                 | X                 | X                 | X                 | X                 | X                 | X                 | X                 | X                              |

Abbreviations: 6MWT= 6-minute walk test; AE=adverse event; CT= Computed tomography; DLCO= Diffusion capacity of the lung for carbon monoxide; ECG= electrocardiogram; GM-CSF=granulocyte macrophage colony stimulating factor; GRH=Global rating of health; LRTI-VAS= lower respiratory tract infection-visual analogue scale; QoL-B= Quality of Life- Bronchiectasis

a Procedures marked with brackets should be performed as necessary.

b 6MWT includes assessment of SpO2 and Borg CR10 score for dyspnea before, during (SpO2) and after (Borg) the test.

c Three samples, preferably on consecutive days, will be collected. All samples collected at V9, V11 and V13 will home collected.

d Sample to be taken before dosing at the site.

e A chest X-ray not a study requirement. But if subjects have a chest X-ray during the study period as part of the local routine clinical practice, the results from the X-ray will be recorded.

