#### 13.1. Primary Endpoint

- Sputum culture conversion defined as at least three consecutive negative sputum samples during the treatment period.

The time of culture conversion is defined as the time the first of three consecutive negative samples was obtained.

Sputum culture conversion rates (number of patients who convert to negative out of the number per group) will be presented with 95% exact binomial confidence intervals.

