2. PROJECT OVERVIEW

2.1 Study Design

This is an open-label, non-controlled, multicentre, pilot clinical trial of inhaled molgramostim in subjects with persistent pulmonary NTM infection.

The study will comprise a Screening Visit, Baseline Visit, a 48-week treatment period and a 12-week follow up period. The Screening Visit (Visit 1) will be conducted up to 10 weeks prior to the Baseline Visit (Visit 2) to determine eligibility. Adult subjects with a history of chronic NTM infection with at least 2 positive cultures in the prior two years, of which at least one is within the last 6 months prior to Screening, will be considered for enrolment. Subjects should provide a positive NTM sputum culture at Screening to be eligible.

The study will include 30 subjects.

The treatment period will consist of 14 trial visits (Screening, Baseline, and at Weeks 4, 8, 12, 16, 20, 24, 28, 32, 36, 40, 44, and 48; Visits 1-14) and a follow-up visit (Visit 15) 12 weeks after end of treatment. The visits at Weeks 28, 36 and 44 (Visits 9, 11 and 13) will include a telephone contact, all other visits will include a clinic visit.

At the Baseline Visit (Visit 2), eligible subjects will start treatment with inhaled molgramostim administered via the PARI eFlow nebulizer.

At each visit (Visits 1-15), sputum samples for staining and microscopy, and microbiological culture will be collected. If required, induced sputum may be obtained according to local standards. On the days of clinic visits (Visits 1, 2, 3, 4, 5, 6, 7, 8, 10, 12, 14 and 15), subjects will be asked to collect two additional sputum samples at home, preferably on the consecutive days after the site visit (At the commencement of the study, only 1 sample was required for Visits 2 to 7, with the additional sampling added in protocol amendment(s)). On the days of the telephone contact visits (Visits 9, 11 and 13), three sputum samples will be collected at home, preferably on consecutive days.

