9.2 Variables

9.2.1 *Primary Endpoint Variables*

- Sputum culture conversion during the treatment period defined as all available samples from three consecutive visits to be negative
- The time of culture conversion: Defined as the time the first of three consecutive visits with 100% negative samples was obtained. Subjects with no conversion will be censored at the date of their last visit.

9.2.2 *Secondary Endpoint Variables*

- Sputum smear conversion: Defined as at least three consecutive visits with 100% negative AFB stained sputum smears on microscopy during the treatment period in subjects that were smear positive at Baseline.
- Durability of sputum culture conversion: Defined as conversion at or before Week 48 and culture still negative at 12-weeks follow-up (with no positives in between).
- Durability of sputum smear conversion: Defined as conversion at or before Week 48 and smear still negative at 12-weeks follow-up (with no positives in between).
- Change from baseline in semi-quantitative grade of number of NTM on microscopy of AFB stained sputum smears
- Change from baseline in semi-quantitative grade of sputum cultures (measured by time to positivity and exploratory quantitation of cultures)
- Change from baseline in symptom scores
 - Lower Respiratory Tract Infections – Visual Analogue Score (LRTI-VAS)
 - Quality of Life Questionnaire – Bronchiectasis (QOL-B)
- Change from baseline in Global Rating of Health (GRH)
- Change from baseline in body weight
- Change from baseline in 6MWD, oxygen desaturation and Borg CR10 scores

9.3 **Biostatistical methods**

9.3.1 *Primary Endpoint*

9.3.1.1 *Sputum Culture Conversion*

Sputum culture conversion data will be listed, including time of culture conversion.

Sputum culture conversion rates (number of subjects who convert to negative out of the number per group) will be presented with 95% exact binomial confidence intervals.

On the basis of the poor historical success rates of current standard therapy, a 30% response rate for the primary endpoint will be considered clinically relevant.

Time to culture conversion will be evaluated using Kaplan Meier estimates, with 95% confidence intervals.

9.3.1.2 *Sensitivity Analyses*

In a sensitivity analysis, culture conversion will be re-defined as requiring at least 2 samples are available from each of the three consecutive visits. Sputum culture conversion rates and time to culture conversion will be analysed as part of this sensitivity analysis.

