12. HANDLING OF MISSING DATA

Only recorded data will be analysed/presented and any subjects who have missing data will only have observed data reported, with no imputation for missing data.

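### The primary endpoint has two non-equivalent definitions (three negative samples, or three all-negative visits), and the SAP does not declare the change from the protocol

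*SAP*

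**What the plan says.** **Sample rule.** Protocol 7.3.1.1 and 13.1 and SAP 9.1.1 share one wording: "Sputum culture conversion defined as at least three consecutive negative sputum samples during the treatment period". Protocol 13.1 dates the event accordingly: "The time of culture conversion is defined as the time the first of three consecutive negative samples was obtained".

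**Visit rule.** SAP 9.2.1 gives the primary variable as "Sputum culture conversion during the treatment period defined as all available samples from three consecutive visits to be negative". Its date of conversion is "Defined as the time the first of three consecutive visits with 100% negative samples was obtained". The sensitivity analysis in SAP 9.3.1.2 keeps visits as the unit: "culture conversion will be re-defined as requiring at least 2 samples are available from each of the three consecutive visits".

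**Sampling.** Footnote c to protocol Table 1 reads "Three samples, preferably on consecutive days, will be collected". SAP 2.1 records that this was not always so: "At the commencement of the study, only 1 sample was required for Visits 2 to 7".

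**Smear conversion.** The same split appears. SAP 9.1.2 and the smear bullet of SAP 14 count a run of smears, while SAP 9.2.2 counts visits.

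**Declared changes.** SAP 13 lists the replacement of the 5x5 grading tables, and 13.1 adds the interim analysis. Neither mentions the conversion rule or its date.

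**The concern.** With one specimen per visit, a run of three negative samples and a run of three negative visits are the same thing. With three specimens per visit they are not. The sample wording can then be met within about three days, by specimens from one visit. The visit wording needs negativity sustained from the first to the third of three 4-weekly visits, about 8 weeks.

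SAP 9.3.1.1 gives the conversion rate and its exact confidence interval without saying which rule feeds them. Time to conversion and the durability endpoints inherit the ambiguity. The trial has no control group, so the rate is read directly against the 30% level in SAP 9.3.1.1. Someone who reads the protocol or SAP 9.1.1 will take the reported rate to be a more lenient endpoint than the one SAP 9.2.1 produces.

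There is also a gap in the visit rule itself. It sets no minimum number of results for a visit to count as negative. SAP 12 says "any subjects who have missing data will only have observed data reported, with no imputation for missing data", which suggests that at least one result is needed, but this is not stated.

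**Working it through.** The plan has no figure to reproduce, because no formal sample size calculation was done. The check is whether the two rules agree and, if not, by how much they can differ.

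**Step 1: one subject.** Take three negative samples at Week 8 and positive samples at all other visits. The sample rule finds a run of three, so the subject converts. The visit rule finds one all-negative visit, so the subject does not convert. No assumption is needed.

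**Step 2: all patterns.**

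| Layout | Patterns | Both rules | Sample rule only | Visit rule only | Neither |
|---|---|---|---|---|---|
| 4 visits x 3 samples | 4,096 | 15 | 2,376 | 0 | 1,705 |
| 12 visits x 1 sample | 4,096 | 2,391 | 0 | 0 | 1,705 |

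If every scheduled visit has at least one result, the visit rule is a subset of the sample rule: three all-negative visits contain at least three negatives in a row. The rules separate only when a visit has more than one sample.

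**Step 3: effect on the rate.** With the planned N = 30, each reclassified subject moves the pooled rate by 1/30 = 3.3 points. As an example, suppose 9 subjects convert under the sample rule and 3 of them qualify only by a run of samples. The Clopper-Pearson 95% intervals are:
- 9/30 = 30.0%, 14.7 to 49.4%
- 6/30 = 20.0%, 7.7 to 38.6%

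The count of three is illustrative. Rates are also to be given per group, where the denominator is smaller and each subject weighs more.

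**Step 4: apparent conversion with no true conversion.** Let q be the chance that a sample from a still-infected subject is culture-negative. The documents give no q, so I assume 0.1, 0.2 and 0.3. The result is the exact Markov-chain probability of at least one run of three. Under the sample rule each trial is one sample, with probability q. Under the visit rule each trial is one visit, with probability q for one sample or q³ for three. There are 12 post-baseline treatment visits (Weeks 4 to 48).

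| Scenario | Rule | q = 0.1 | q = 0.2 | q = 0.3 |
|---|---|---|---|---|
| (a) 12 visits x 3 samples, independent | sample (36 trials) | 3.0% | 20.1% | 50.1% |
| | visit (12 trials at q³) | <0.01% | <0.01% | 0.02% |
| (b) 12 visits x 1 sample | both (12 trials at q) | 0.9% | 6.5% | 18.9% |
| (c) Early cohort: 1 sample at Visits 3-7, 3 at Visits 8-14 | sample (5 + 21 = 26 trials) | 2.2% | 14.7% | 38.9% |
| | visit (5 at q, then 7 at q³) | 0.3% | 2.1% | 6.7% |
| (d) As (a), q varying between subjects | sample | 13% | 27% | 41% |
| | visit | 2.2% | 5.7% | 10.9% |
| (e) 24 weeks: 6 visits x 3 samples | sample (18 trials) | 1.4% | 10.1% | 28.2% |
| | visit (6 trials at q³) | <0.01% | <0.01% | 0.01% |

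Scenario (d) averages over Beta(q(1/ICC − 1), (1 − q)(1/ICC − 1)) with an assumed ICC of 0.4. In every multi-sample scenario the sample rule gives the higher figure, and in (c) and (d) the visit rule is not negligible.

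**The case against.** The strongest reply is that SAP 9.1 only restates the protocol and SAP 9.2.1 is the working definition. Time to conversion, the smear variable and both sensitivity analyses count visits, and nothing in SAP 9.2 or 9.3 uses the sample rule. The visit rule is written openly and may simply preserve the visit-based meaning that held when one sample was taken per visit. On this view what is missing is one line in SAP 13. Under scheduled sampling the change lowers the rate, and this is a descriptive 30-subject pilot with no test attached to the 30% level.

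Much of this stands. The visit rule is probably intended, and it is conservative. The Step 4 figures rest on an assumed q, and the sample-rule rows apply only if SAP 9.1.1 is what gets programmed. Follow-up limited to 24 weeks, which protocol 8.1 allows, roughly halves them (scenario e). The nesting also has a condition: if an unscheduled positive sample were left out of the visit derivation, it could break a run of samples without breaking a run of visits.

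The contradiction remains. A working definition should implement its endpoint, and this one replaces it with a narrower one. A conservative change to the primary responder rule and its date still has to be declared.

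**Conclusion.** The concern holds, and the plan should be corrected. The SAP carries two rules for its primary endpoint that classify the same subject differently. SAP 9.2.1 departs from protocol 13.1 in both the rule and the date of conversion, and SAP 13 does not say so. No planned analysis reports the endpoint as the protocol defines it. The contradiction rests on no assumption.

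Its size in the data cannot be known from the documents beyond 3.3 points of the pooled rate per reclassified subject. The direction is known: with at least one result at each scheduled visit, and only scheduled samples used, the visit rule gives an equal or lower rate. Since one rule is probably intended and the remedy is mainly wording, this is a should-fix point.

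**What to change.** 1. In SAP 9.1.1 and 9.3.1.1, name the visit-based definition as the single primary rule. Align the smear wording in SAP 9.1.2 and in the smear bullet of SAP 14.
2. State that a visit counts as negative only if it has at least one evaluable result and all its results are negative. Add that a scheduled visit without a result is therefore not negative and interrupts the run.
3. List the new rule and the new date of conversion in SAP 13 as changes from protocol 13.1.
4. Report the protocol's sample-based rule as a sensitivity analysis beside the existing one that requires two samples per visit.

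The cost is a few lines of SAP text, one entry in SAP 13 and one extra table. No new data are needed. Under scheduled sampling, the sponsor should expect a primary rate no higher than the protocol's rule would give.

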9.2 Variables

9.2.1 *Primary Endpoint Variables*

- Sputum culture conversion during the treatment period defined as all available samples from three consecutive visits to be negative
- The time of culture conversion: Defined as the time the first of three consecutive visits with 100% negative samples was obtained. Subjects with no conversion will be censored at the date of their last visit.

9.2.2 *Secondary Endpoint Variables*

- Sputum smear conversion: Defined as at least three consecutive visits with 100% negative AFB stained sputum smears on microscopy during the treatment period in subjects that were smear positive at Baseline.
- Durability of sputum culture conversion: Defined as conversion at or before Week 48 and culture still negative at 12-weeks follow-up (with no positives in between).
- Durability of sputum smear conversion: Defined as conversion at or before Week 48 and smear still negative at 12-weeks follow-up (with no positives in between).
- Change from baseline in semi-quantitative grade of number of NTM on microscopy of AFB stained sputum smears
- Change from baseline in semi-quantitative grade of sputum cultures (measured by time to positivity and exploratory quantitation of cultures)
- Change from baseline in symptom scores
 - Lower Respiratory Tract Infections – Visual Analogue Score (LRTI-VAS)
 - Quality of Life Questionnaire – Bronchiectasis (QOL-B)
- Change from baseline in Global Rating of Health (GRH)
- Change from baseline in body weight
- Change from baseline in 6MWD, oxygen desaturation and Borg CR10 scores

9.3 **Biostatistical methods**

9.3.1 *Primary Endpoint*

9.3.1.1 *Sputum Culture Conversion*

Sputum culture conversion data will be listed, including time of culture conversion.

Sputum culture conversion rates (number of subjects who convert to negative out of the number per group) will be presented with 95% exact binomial confidence intervals.

On the basis of the poor historical success rates of current standard therapy, a 30% response rate for the primary endpoint will be considered clinically relevant.

Time to culture conversion will be evaluated using Kaplan Meier estimates, with 95% confidence intervals.

9.3.1.2 *Sensitivity Analyses*

In a sensitivity analysis, culture conversion will be re-defined as requiring at least 2 samples are available from each of the three consecutive visits. Sputum culture conversion rates and time to culture conversion will be analysed as part of this sensitivity analysis.

9.3.2 *Secondary Endpoints*

9.3.2.1 *Sputum Smear Conversion (Primary)*

Sputum smear conversion will be evaluated and presented in the same way as the primary endpoint for culture conversion.

9.3.2.2 *Sputum Smear Conversion (Sensitivity)*

In a sensitivity analysis, smear conversion will be re-defined as requiring at least 2 samples are available from each of the three consecutive visits. Sputum smear conversion rates and time to smear conversion will be analysed as part of this sensitivity analysis.

9.3.2.3 *Mycobacterial Microscopy Grading*

Mycobacterial microscopy data will be listed for each sample, including AFB positivity and AFB semi-quantitative grading. The listing will also include the overall visit AFB positivity and grading statuses. Laboratory grading terminology will be re-named as detailed in Table 4.

Table 4: *Mycobacterial Microscopy Grading*

SNP	RBH	Cross-Tabulation
No acid fast bacilli seen	No AFB Seen	Negative
Acid fast bacilli – occasional	Scanty AFB Seen +/-	Scant
Acid fast bacilli +	Moderate AFB Seen 1+	1+
Acid fast bacilli ++	Moderate AFB Seen 2+	2+
Acid fast bacilli +++	AFB Seen 3+	3+
Acid fast bacilli ++++		4+

The number of subjects who decrease over the scale (and proportion out of the number per group) will be presented with 95% exact binomial confidence intervals.

A summary table will present continuous descriptive statistics of grade for each scheduled visit.

9.3.2.4 *Mycobacterial Culture Grading*

Mycobacterial culture data will be listed for each sample, including culture positivity, culture semi-quantitative grading, time to detection in liquid media (MGIT) and organisms isolated. The listing will also include the overall visit AFB positivity and grading statuses.

The following is noted:

- MGIT and semi-quantitative grading will need to be extracted from the Comment column in the SNP data transfer.
- Semi-quantitative grading is not available for mycobacterial culture data from RBH.

For each scheduled visit, the number of subjects (and proportion out of the number per group) who report a decreased culture grade compared to Baseline will be presented with 95% exact binomial confidence intervals. Where multiple samples were taken at a visit, the worst grade will be used for comparison to Baseline.

A figure will present the mean change from baseline of semi-quantitative sputum culture grades, with error bars representing the standard deviation.

9.3.2.5 *Symptom Scores*

Symptoms scores (assessed using LRTI-VAS and QOL-B) will be listed for all subjects.

Scoring of LRTI-VAS

Separate scores will be calculated for each symptom and a total score will be calculated, consisting of all symptom scores added up, where the same weight is assigned to all symptom domains.

Symptom and total scores will not be calculated for LRTI-VAS records with missing data.

A summary table will present a summary of total scores, including actual values and change from Baseline, by group and overall, for all scheduled visits.

Scoring QOL-B

QOL-B data will be scored according to the Manual Scoring Instructions for QOL-B Version 3.1 and domain scores will be presented in a separate listing.

A summary table will present a summary of domain scores, including actual values and change from Baseline, by group and overall, for all scheduled visits.

9.3.2.6 *Global Rating of Health (GRH)*

Global Rating of Health (GRH) data will be listed for all subjects.

A summary table will present a summary of actual values and change from Baseline, by group and overall, for all scheduled visits.

9.3.2.7 *Body Weight*

Body weight will be listed for all subjects.

A summary table will present a summary of actual values and change from Baseline, by group and overall, for all scheduled visits.

9.3.2.8 *6 Minute Walk Test*

6 Minute Walk Test data, including distance walked (6MWD), oxygen saturation (SpO₂) before and during the test as well as oxygen desaturation (delta SpO₂) and Borg (CR-10) Dyspnoea scores before and after the test, will be listed for all subjects.

A summary table will present a summary of actual values and change from Baseline, by group and overall, for all scheduled visits, for the following variables:

- Dyspnoea Score (Borg CR-10) (pre and post walk)
- Blood oxygen saturation (SpO₂) pre walk
- Worst SpO₂ during the walk
- Distance walked

The proportion of subjects that complete all 6 minutes walking during the test will be summarised for all scheduled visits.

Where the two scheduled 6MWT tests were performed at a given scheduled timepoint, the summary table will use the data from the assessment where the subject walked the longest distance.

